4 STUDY SCHEDULE

Assessments:

After written consent is received, participant's demographic baseline information at entrance to the trial will be recorded. 5 of the KTx recipients and 2 of the HCP will undergo 'Think-aloud' interviews to assess the usability of the exertion resource. Usability is defined as how

easily someone can use and interact with the online system without any formal training (13). ‘Think-Aloud’ interviews are a qualitative research technique that assesses how the user interacts with the system and a sample of five can uncover 80% of usability problems and issues (13). ‘Think-aloud’ interviews provide a valid source of data concerning participant thinking as the participant is asked to vocalise as they perform a task, supervised by the researcher (14). Therefore in this study, the main researcher will record verbatim from participants as they talk out loud whilst accessing and using the exertion resource. The researcher will also record field observation notes during the think aloud interviews. Verbal speech and site log in data will be recorded from these sessions. We estimate these interviews will take 60-90 minutes.

The remaining participants (5 KTx and 3 HCP), will have the same amount of time reviewing the resource at the start of the session (60-90 minutes). After the ‘Think-aloud’ interviews or review of resources, participants will complete a one-on-one semi-structured interview to review their thoughts and experiences on using the exertion resource. Please refer to summary of study flow diagram on page 5 and schedule of assessment (Table 1) below. Having the semi-structured interviews on the same day as the ‘Think-aloud’ interviews or the reviewing of the resource will minimise patient burden and recall bias.

Table 1- Schedule of Assessment

Procedure	Recruitment	Visit 1
Screening and informed written consent	X	
Medical history and demographics		X
‘Think-Aloud’ interviews: - 5 KTx - 2 HCP - Estimate 60-90 minutes total		X
Exposure to the resource lab sessions Estimate 60-90minutes total		X
Semi structured individual interviews (n=9 KTx, n=5 HCP)		X

4.1 Distress protocol

As participants will be discussing exercise and food intake whilst using the online resource and during the semi-structured interviews the team have devised a distress protocol (modified from Distress Protocol for qualitative data collection, C.Haigh and G. Witham, Department of Nursing Manchester Metropolitan University).

[figure not shown]

Figure 2. Distress Protocol

Participants if willing to participate will be consented as per the GCP guidelines. Only adults above the age of 18, with capacity to consent will be accepted into the study. Non-english speakers will be consented via language-line phone translation service. The participant and responsible clinician will sign the informed consent form and the responsible clinician will perform a final confirmation of eligibility. Informed consent will be obtained before any trial-related procedures are undertaken. A copy of the signed informed consent form will be given to the participant. The original signed form will be retained at the study site in the Investigator Site File and a copy placed in the medical notes. A copy will also be sent to the Chief Investigator of the study. With KTx participant's prior consent, their General Practitioner (GP) will also be informed of their participation of the study.

6 ELIGIBILITY CRITERIA

Participants will be included based on the following inclusion and exclusion criteria. Those who are ineligible, or decline to participate will be captured on the secure and encrypted recruitment and screening log.

6.1 Eligibility criteria for the KTx recipient participants (n=10)

6.1.1 Inclusion criteria:

- Adult patient (18 years+)
- male or female
- Able to provide written informed consent
- < 3 months post-transplant. NB. Our team has decided to recruit patients within the first three months post transplants as most patients at our centre are not cleared to start a formal physical activity or exercise plan until they have ureteric stents removed which usually occurs at 6 weeks post-transplant surgery.
- Access to Internet connected computer, smart-phone or tablet. NB. Our team has completed a waiting room survey and our patients often use internet to view their clinical blood results through "renal patient view", therefore do not perceive internet access as a barrier to this study.
- A Body Mass Index (BMI) greater than or equal to 18.5 (healthy range).

6.1.2 Exclusion criteria:

- Age < 18 years of age
- Pregnancy

- Unstable medical conditions such as angina, uncontrolled hypertension or diabetes, congestive cardiac failure, active myocarditis, cardiac arrhythmia, co-morbid catabolic condition, psychiatric illness.
- Participated in a structured exercise or physical activity intervention in the last three months
- BMI of less than 18.5 (classified as underweight)
- Significant cognitive impairment preventing them from engaging with online interactive material

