2.2 Secondary Objectives

a) To explore the current themes through qualitative data collection:

- Components of the “exertion” resource that are helpful/ unhelpful
- Any difficulties/ barriers to using the “exertion” application

- Any difficulties/ barriers to participating in the study?
- Strengths of the “exertion” resource
- Weaknesses of the resource
- Patient experience and learning using the online resource
- Transplant health care professional experience and knowledge reviewing the online resource

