(physical activity) and reduce fear avoidance (using basic acceptance and commitment therapy principles). Tailored feedback will include encouragement and virtual rewards if maintaining weight. Weight gain will trigger initial referral to an automated recovery package. This package will be built into the interventional platform and automatically activate given an increase in weight. The nature of this package is to ensure that following weight gain, the patient remains engaged with this interventional programme and will provide additional behavioural support. The online tool will be accessible either online, or via a smart phone or tablet as a health application (app).

We plan for the resource to allow participants to select modules to work through on a monthly basis over a 12 month period. Behavioural change tools and resources will be embedded within the “exertion” resource. For this current study, participants will access the online exertion resource at a one off supervised research visit. Participants will not have exposure or access to this online resource outside this study visit. The main modules will include information and interactive text on the following areas:

1. Managing cravings and prednisolone
2. Goal setting for activity and food planning
3. Portion sizes and the NHS healthy plate
4. Patient examples of strategies to plan activity (physical activity planning)
5. Patient examples of strategies to eating out/ holidays with low fat diets (food planning)
6. Reading food labels and making healthy food choices
7. Identifying barriers
8. Problem solving
9. Relapse prevention
10. Planning for the future

To ensure the modules are interactive, participants will be asked questions relating to:

- Number of steps and self-reported physical activity levels
- Weight, height, BMI
- Portion sizes
- Individual SMART goals regarding food and activity. The participants will be asked if they have achieved these set goals.
- Problem solving questions for activity and food
- Rating the importance and confidence in ability to make changes to food an activity using a VAS (visual analogue scale)

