8 STATISTICAL METHODS

8.1 Sample Size

We will interview a purposive sample of KTx patients to include a range of gender and age. We will aim to also recruit a purposive sample of kidney transplant HCP. ‘Think-aloud’ interviews produce large amounts of rich data and it is suggested that site 80% of usability problems are identified with 5 think aloud interviews. Therefore this research team aims to do think aloud interviews on 5 KTx recipients and 2 HCPs.

Individual semi-structured interviews will utilise appropriate topic guides that will be developed and discussed with the patient advisory group, and the steering group. We will continue with individual interviews until we reach data saturation, there is no new data, no new themes, no new coding and we are able to replicate the study (15, 16).

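### Cheap improvement: add digital confidence to the KTx purposive frame, because a sample made up only of confident internet users would meet the plan and could under-report barriers to use

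*Combined protocol and SAP*

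**What the plan says.** Section 2.2 lists among the secondary objectives "Any difficulties/ barriers to using the" application. Section 3.1 adds, as think-aloud themes, barriers, sections that are easier to use, and differences between individuals in how they use the resource. Section 4 defines usability as ease of use for someone who has not been formally taught the system.

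Who supplies this information is set in two places:

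- **Entry (section 6.1.1).** A KTx patient needs "Access to Internet connected computer, smart-phone or tablet". The reason given is "Our team has completed a waiting room survey and our patients often use internet to view their clinical blood results", and the team "therefore do not perceive internet access as a barrier to this study". A separate exclusion covers "Significant cognitive impairment preventing them from engaging with online interactive material".
- **Sampling (section 8.1).** "We will interview a purposive sample of KTx patients to include a range of gender and age". No other patient characteristic is named. For the professionals the text says only "We will aim to also recruit a purposive sample of kidney transplant HCP".

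Ten KTx patients are planned. Five do think-aloud interviews and five review the resource without one (section 4). No rule says which patients go to which group. All use is supervised: "Participants will not have exposure or access to this online resource outside this study visit" (section 3.2).

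**The concern.** If usability is ease of use without training, a patient's prior confidence with online tools bears directly on what the interviews will show. The sampling frame is silent on it. The plan could be followed to the letter with ten patients who all find websites easy, and the interviews would then report few difficulties.

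The survey sentence does not close this gap. It says that patients often use the internet, with no number surveyed and no percentage, so it does not describe those who do not.

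Section 1 says that the results will refine the resource and lead to a randomised feasibility trial. A difficulty that nobody in the sample meets would be carried into that version.

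**Working it through.** **Inputs**

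- KTx patients: 10, of whom 5 do think-aloud interviews (sections 3.1, 4 and 8.1).
- Share of usability problems found with five think-aloud interviews: 80% (sections 4 and 8.1).
- Share of eligible patients with low digital confidence, *s*: not in the documents. Assumed to be 10%, 20% or 30%.

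**1. The plan's own figure.** The usual problem-discovery model is P(seen at least once) = 1 − (1 − p)^n, where p is the chance that one user meets the problem. The documents give no p, so the 80% cannot be reproduced independently. Solved backwards, p = 1 − 0.2^(1/5) = 0.275, which returns 80% at n = 5. This shows consistency only. It also assumes that every participant could meet every problem.

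**2. Chance that no low-confidence user is sampled.** Treating selection as independent random draws, P(none) = (1 − s)^n.

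| s (assumed) | five think-aloud patients | all ten KTx patients |
|---|---|---|
| 10% | 0.9^5 = 0.590 | 0.9^10 = 0.349 |
| 20% | 0.8^5 = 0.328 | 0.8^10 = 0.107 |
| 30% | 0.7^5 = 0.168 | 0.7^10 = 0.028 |

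Both columns matter, because difficulties are explored in the semi-structured interviews as well as in the think-aloud sessions.

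**3. Chance of seeing a problem that only low-confidence users meet.** Replace p by s × p in step 1, with n = 5 and p = 0.275 (back-solved):

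- s = 10%: 1 − (1 − 0.0275)^5 = 13%
- s = 20%: 1 − (1 − 0.0550)^5 = 25%
- s = 30%: 1 − (1 − 0.0826)^5 = 35%

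The cited figure is 80%. If one or two of the five think-aloud patients were known to be low-confidence users, the chance would be 1 − (1 − 0.275) = 27.5% or 1 − (1 − 0.275)^2 = 47.5%. These figures are illustrative, since they rest on a back-solved p.

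**4. Patients without access.** Their share of the sample is zero by design. A difficulty specific to them cannot be observed directly at any sample size.

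**The case against.** **Access is not confidence.** A reader might infer that the entry and sampling rules remove low-confidence users. They do not. Section 6.1.1 asks for access, not ownership, skill or past use, so a hesitant patient with a smartphone is eligible. The sampling rule removes nobody; it only fails to ensure that such patients are included. This objection stands.

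**The survey note is about the study.** A reader might take "therefore do not perceive internet access as a barrier to this study" as a finding that access is no barrier to using the resource. The sentence speaks of a barrier to the study. Barriers to the resource remain an open question in sections 2.2 and 3.1.

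**The access rule fits an online product.** It is reasonable to test usability in people who could use the tool. The supervised single visit shows no study procedure that needs the patient's own device, but that alone does not make the criterion wrong. A centre device could also bring unfamiliarity that is no fault of the resource.

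**The figures rest on assumptions.** The shares are assumed, and the sample is purposive, not random. A range of ages may partly track digital confidence and so lower the probabilities.

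**The plan has partial safeguards.** Section 8.2 uses deviant case codes, section 8.1 continues interviews to saturation, section 5 allows non-English speakers to consent, and sections 6 and 7.1 log ineligible patients. These help, but do not close the gap. Deviant case coding works only on people already sampled, saturation can be reached within a narrow sample, and no analysis of the log is planned.

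**Weight status.** A reader might want BMI bands in the frame too. Nothing in the documents ties BMI to ease of use, so the point does not extend there.

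**Conclusion.** The point holds as a cheap improvement to the sampling frame, not as a flaw that invalidates the study. Low-confidence users with device access need not be sampled, although the study aims to learn about barriers and individual differences. Patients without access are not heard at all.

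Over the assumed range of 10% to 30%, the chance of missing low-confidence users altogether runs from 59% down to 17% for the five think-aloud patients, and from 35% down to 3% for all ten. This treats selection as random and makes no allowance for the age range. If low confidence is common, the ten patients together will probably include someone who has it. The weaker spot is the think-aloud group, where usability is observed directly.

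The documents do not support the stronger conclusions that the usability findings are invalid or that the access criterion should go. What follows is that the barrier findings apply to patients with internet access, and may under-report difficulties within that group.

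**What to change.** 1. In section 8.1, add self-rated digital confidence to gender and age in the KTx purposive frame, using one screening question.
2. Aim to include low-confidence users both among the five KTx think-aloud patients and among the other five. State this as a target, not a hard quota, because several characteristics must be spread over very few patients.
3. Keep the access criterion in section 6.1.1. Report from the existing screening log how many patients were ineligible for lack of access.
4. Limit the barrier conclusions to patients with internet access.

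**Cost.** One question and one line of reporting, with no extra participants or visits. Recruitment within the 3-month test period may be somewhat slower. Finding two low-confidence patients, one for each group, means asking on average 2/0.10 = 20 eligible patients if the share is 10%, or 2/0.20 = 10 if it is 20%, before allowing for refusals. This is a further reason for a target. A single self-rated question is also a rough measure, adequate for spreading a sample but not for classifying patients.

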6.2 Eligibility criteria for the Transplant Health Care Professionals (n=5)

6.2.1 Inclusion criteria:

- A nephrologist, kidney doctor, nurse or member of the multi-disciplinary team who actively work with kidney transplant patients at King's College Hospital
- Adult above 18 years of age
- Able to provide written consent
- Access to Internet connected computer, smart-phone or tablet.

6.2.2 Exclusion criteria:

- Pregnancy
- Unstable medical conditions such as angina, uncontrolled hypertension or diabetes, congestive cardiac failure, active myocarditis, cardiac arrhythmia, co-morbid catabolic condition, psychiatric illness.

7 RECRUITMENT

7.1 Selection of Participants

All participants will be recruited from King's College Hospital renal outpatients. Potential participants will be identified when presenting for their routine post-transplant hospital clinic visits by the transplant clinical team. Patients who fulfil the inclusion criteria will have their eligibility confirmed by the research team. Each patient must meet all of the inclusion criteria, and none of the exclusion criteria at entry to the trial. After confirming eligibility, eligible patients will be approached by an appropriately trained member of the research team who routinely work in the transplant clinic, to ascertain interest in entering the study. This individual (likely to be either the PI or CI of the study) will give a comprehensive verbal explanation of the trial (explaining both the investigational and standard treatment options and highlighting any possible benefits or risks relating to participation). Time for questions throughout the discussion will be given and questions adequately addressed. Potential participants will also be given a written information sheet about the trial and be given sufficient time (providing they have received the patient information sheet and had at least 24 hours to read and fully understand the implications of the trial) to consider the study

information prior to deciding whether to take part. Participants that agree to enter the study will then be asked to consent to undergo study assessments. If the participant is willing to take part then they will be asked to sign the consent form with a member of the research team countersigning. Screening logs will be kept on the secure “renal physio” drive and will be encrypted for confidentiality. All eligible and ineligible patients, plus those declining to participate will be logged on the secure screening log.

Throughout the trial duration, participants will be encouraged to ask questions and will be reminded that they can withdraw at any time without their clinical care being affected. **No payment is to be offered to the participants taking part in the trial.**

8 STATISTICAL METHODS

8.1 Sample Size

We will interview a purposive sample of KTx patients to include a range of gender and age. We will aim to also recruit a purposive sample of kidney transplant HCP. ‘Think-aloud’ interviews produce large amounts of rich data and it is suggested that site 80% of usability problems are identified with 5 think aloud interviews. Therefore this research team aims to do think aloud interviews on 5 KTx recipients and 2 HCPs.

Individual semi-structured interviews will utilise appropriate topic guides that will be developed and discussed with the patient advisory group, and the steering group. We will continue with individual interviews until we reach data saturation, there is no new data, no new themes, no new coding and we are able to replicate the study (15, 16).

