8.2 Statistical Analysis

Baseline demographics of the patients will be described using summary statistics. Continuous variables will be summarised using the mean and standard deviation (SD) if approximately normally distributed. Continuous variables that are not normally distributed will be summarised using the median and IQR.

Qualitative analysis: Data will be collected through in-depth feedback about our online intervention materials; field notes, individual interviews and ‘Think-aloud’ interviews. ‘Think-aloud’ interviews will be used to elicit participants’ reactions to sessions of the online intervention; participants will be observed and asked to comment aloud on reactions to every aspect of the different sessions. Semi-structured interviews will explore participants’ overall impressions of the online intervention. These qualitative techniques will allow for themes and sub-themes to emerge. The website will be designed to record user entries, and observational field notes about participants’ use of the intervention will also be collected. Individual interviews will be transcribed verbatim and analysed using an inductive thematic analysis approach (17), informed by techniques of grounded theory (15), including line-by-line open coding grounded in data and constant comparison of all instances of codes. Deviant case codes will be employed to ensure that perspectives that diverge from dominant trends are not overlooked.

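### Does sizing the think-aloud interviews by usability problems found, while planning only a thematic analysis, leave the refine phase without a usable result?

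*Combined protocol and SAP*

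**What the plan says.** Section 4 has 5 kidney transplant (KTx) recipients and 2 HCPs take part in think-aloud "interviews to assess the usability of the exertion resource". It defines usability as ease of use without formal training and cites the benchmark that "a sample of five can uncover 80% of usability problems and issues". Section 8.1 repeats the benchmark ("it is suggested that site 80% of usability problems are identified with 5 think aloud interviews") and draws the numbers from it: "Therefore this research team aims to do think aloud interviews on 5 KTx recipients and 2 HCPs".

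Section 8.2 uses the think-alouds to draw out reactions to each part of the sessions. On output it says: "These qualitative techniques will allow for themes and sub-themes to emerge". On method it says: "Individual interviews will be transcribed verbatim and analysed using an inductive thematic analysis approach", with line-by-line open coding and constant comparison. It adds: "Deviant case codes will be employed to ensure that perspectives that diverge from dominant trends are not overlooked". On other data it says: "The website will be designed to record user entries", and it has field notes taken on how participants use the resource.

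The introduction says the results will refine the resource, and section 3.1 sets aside 3 of the 9 months for this.

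**The concern.** The unit that justifies five interviews is the usability problem, and that unit does not reappear in section 8.2. Usability is defined, but a usability problem is not. Nothing says that problems are listed, which participant or group met each one, or how a problem leads to a change. User entries and log-in data are collected with no stated analysis. Read literally, the analysis sentence names individual interviews, although 8.2 lists these separately from the think-alouds.

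Refinement is the purpose of the study. A theme can merge several distinct faults, and a fault met by one person is not obviously a divergent perspective of the kind that deviant-case coding protects. If such items dropped out, the refine phase would work from an incomplete picture, and a later feasibility trial would test a resource with avoidable faults. The basis for the 2 HCP think-alouds would also stay open.

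**Working it through.** **1. The plan's figure.** The documents give 80% at n = 5 but no formula and no detection probability p, so the figure cannot be derived independently. As a consistency check, assume that participants detect problems independently with equal probability p. The share found is then 1 − (1 − p)^n. Setting this to 0.80 at n = 5 gives p = 1 − 0.2^(1/5) = 0.275, which returns 80% by construction.

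**2. What the benchmark covers.** At p = 0.275, two interviews find 1 − 0.725² = 47% and seven find 1 − 0.725⁷ = 89% (if both groups meet the same problems). For two HCPs alone to reach 80%, p would have to be 1 − 0.2^(1/2) = 0.553. The benchmark therefore supports the 5 KTx interviews, and the 2 HCP interviews are supplementary.

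**3. Problems with a single source.** Under equal detectability, the share of all problems met by exactly one of five is 5p(1 − p)⁴ = 0.380. As a share of those found, this is 0.380/0.80 = 47%. If p varies across problems as a Beta(a, b) distribution, with the 80% at n = 5 held fixed:

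| a + b | SD of p | Single-source share of problems found | Gain from interviews 6 and 7, relative to the KTx list |
|---|---|---|---|
| equal p | 0 | 47% | 11.9% |
| 20 | 0.10 | 41.9% | 10.4% |
| 5 | 0.20 | 31.9% | 8.0% |
| 2 | 0.29 | 22.6% | 5.8% |
| 1 | 0.35 | 15.6% | 4.1% |
| 0.5 | 0.39 | 9.7% | 2.7% |

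The equal-p gain is (0.055 + 0.040)/0.80 = 11.9%.

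**4. What these figures show.** They show how many problems might rest on one participant. They say nothing about how many a thematic analysis would drop. For that, compare the feared loss with the text:

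- *Single remarks.* Line-by-line coding and constant comparison in 8.2 work on every instance, and the think-alouds ask for comment on every aspect of the sessions.
- *Items met by one person.* Section 3.1 makes individual differences in use a target of the think-alouds, alongside the deviant-case codes.
- *Difficulties as an output.* Section 2.2 lists barriers to use, unhelpful components and weaknesses. Section 3.1 adds likes and dislikes, barriers and recommendations.
- *Group.* Section 3.1 lists functionality and interpretation separately for KTx recipients and HCPs. Section 11 replaces patient identifiers with trial ID numbers, so coded material can be traced to a participant.
- *Think-aloud transcripts.* Section 11 has all interviews transcribed, and 8.2 names the think-alouds among its qualitative data, so the narrow reading of the analysis sentence is unlikely to be the intended one.

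**5. Whether a problem log would answer the two numerical questions.** The 80% is found problems divided by all problems. A log supplies the numerator only; the denominator would have to be extrapolated from a few users under a model.

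For HCP-specific problems, the signal would be a gain from the 2 HCPs above the expected 3% to 12%. Simulating equal p = 0.275, with HCPs meeting exactly the same problems as patients, the central 95% range of that gain is 0% to about 40% with an assumed 15 problems, 0% to 33% with 25, and 3% to 28% with 40. An observed gain well above 12% would be unremarkable with no HCP-specific problems at all.

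**The case for a change.** The strongest case for a change is that the plan itself chose a problem-count benchmark, so asking for problems to be listed does not impose a foreign standard on qualitative work. The list of topics in section 3.1 says what to explore and keeps no record of who met which fault or what was done about it. A short definition and a table would need no extra participants or visits.

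Part of this stands. The text does not say how coded difficulties are compiled or linked to changes, and it states no analysis of user entries and log-in data. What does not stand is the step from there to a consequence. No problem is shown to be lost and no conclusion is shown to be wrong. The material for a list is collected in any case, and a team spending three months refining its own resource will work through its coded difficulties. A log can be compiled from transcripts and field notes at that stage.

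In section 3.1, the lead-in to the think-aloud themes mentions 10 recipients and 5 HCPs. This is a clerical slip: the same section already gives 5 and 2 for the think-alouds, as do sections 4 and 8.1.

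**Conclusion.** No change is needed. Sections 4 and 8.1 justify the 5 KTx think-alouds by usability problems found, and section 8.2 describes its output in other terms. This is a gap in reporting detail that the analysts can fill sensibly from data they already plan to hold.

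The 80% is a cited rationale for a small sample and not a result the study sets out to verify, so being unable to check it costs nothing. That it does not carry over to the 2 HCPs changes no result, since no detection rate is claimed for them separately.

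The 10% to 47% single-source share rests on the plan's 80% at n = 5, independent detection and an assumed spread of detectability; it measures exposure and not loss. The simulated ranges in the HCP comparison also rest on equal detectability and an assumed 15 to 40 problems. The conclusion is limited to the text provided: the topic guides are still to be developed and the figures are not shown.
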